3.1.2. Secondary

- To assess the clinical response of early empiric antifungal therapy with fluconazole at Day 22 in subjects with coccidioidomycosis pneumonia regardless of adherence with the study intervention.
- To assess the clinical response of early empiric antifungal therapy with fluconazole at Day 43 in subjects with coccidioidomycosis pneumonia regardless of adherence with the study intervention.
- To compare the clinical response and its individual components over time, by treatment group, in subjects with coccidioidomycosis pneumonia.
- To assess the impact of early empiric antifungal therapy with fluconazole on days lost from work or school and responses to the SF-12v2 and PROMIS Item Bank v2.0 - Ability to Participate in Social Roles and Activities - Short Form 4a in subjects with coccidioidomycosis pneumonia.
- To assess the effect of early empiric antifungal therapy with fluconazole through Day 43 in subjects with coccidioidomycosis pneumonia on all-cause mortality by treatment group.
- To assess whether early empiric antifungal therapy with fluconazole at Day 22 is non-inferior to placebo as defined by clinical response at Day 22 in all randomized subjects, regardless of coccidioidomycosis pneumonia status or adherence with study intervention, with baseline and follow-up FLEET-CAP scores.

3.1.3. Exploratory

- To assess the effect of early empiric fluconazole therapy on the immune response to coccidioidomycosis in subjects with suspected coccidioidomycosis pneumonia.
- To assess the effect of early empiric fluconazole therapy on the development of extrapulmonary symptoms associated with coccidioidomycosis pneumonia.

-
- To assess the effects of early empiric fluconazole therapy on the occurrence of disseminated coccidioidomycosis in subjects with pneumonia in coccidioidomycosis-endemic areas.
 - To characterize the natural history of coccidioidomycosis disease by examining the clinical response and its individual components over time, in placebo recipients with coccidioidomycosis pneumonia.
 - To assess the clinical response of early empiric antifungal therapy with fluconazole at Day 22 in subjects with coccidioidomycosis pneumonia based on an alternative serologic case definition for coccidioidomycosis pneumonia.
 - To compare the clinical signs and symptoms of community-acquired pneumonia caused by coccidioidomycosis pneumonia with the clinical signs and symptoms caused by non-coccidioidomycosis pneumonia in coccidioidomycosis-endemic areas.
 - To characterize the safety of early empiric antifungal therapy with fluconazole with respect to liver function in subjects with pneumonia in coccidioidomycosis-endemic areas.
 - To assess the adherence to long term self-administration of daily fluconazole or placebo in a clinical trial setting using self-reported adherence and pill count.
 - To assess medication adherence in the active fluconazole arm by measuring fluconazole levels.

3.2. Study Outcome Measures

3.2.1. Primary

- The proportion of subjects who achieve a clinical response at Day 22 in each treatment group.
 - “Clinical response” is defined as at least a 50% reduction in composite FLEET CAP score from baseline.

Efficacy outcome measures are based on a clinical scoring system that allows a constellation of clinical symptoms to be quantified and scored over time: cough, fatigue, chest pain, dyspnea, sputum production, night sweats, fever and hypoxia (see [Table 2](#)). The recall period for symptom assessments will be during the past week, with the exception of fever and hypoxia, which will be measured on the day the FLEET CAP is administered.

Table 2: Modified Scoring System for Evaluating Treatment Response in Early Coccidioidal Pneumonia (FLEET CAP Score)*

Community-Acquired Pneumonia (CAP) SYMPTOMS	Points	Proposed Definition
**Cough	0	No coughing, unaware of coughing or cough only now and then
	1	Occasional coughing (less than hourly)
	2	Frequent coughing (one or more times per hour), interferes with sleep
	3	Almost constant coughing (never free of cough or need to cough), makes sleep almost impossible
***Fatigue	0	Absent
	1	Minimal interference with physical function, no interference with carrying out duties and responsibilities
	2	Interference with carrying out duties and responsibilities
	3	Prevents usual work, school, family or social interactions
Chest pain	0	Absent
	1	Noticeable only when coughing
	2	Noticeable during deep breaths or when coughing
	3	Almost constant, present even when resting, without cough
**Dyspnea (Shortness of breath)	0	None, unaware of any difficulty
	1	Noticeable during strenuous activity
	2	Noticeable during light activity, or when washing or dressing
	3	Almost constant, present even when resting
**Sputum production	0	None, unaware of any difficulty or rarely caused problem
	1	Noticeable as a problem
	2	Causes a great deal of inconvenience
	3	An almost constant problem
Night sweats	0	Absent
	1	Bed clothing (e.g., pajamas) damp
	2	Bedding wet and requires change of bedding or clothing
Fever	0	Less than 37.8°Celsius
	1	37.8° – 38.5°Celsius
	2	38.6 – 39.5° Celsius
	3	Greater than 39.5° Celsius
Hypoxia	0	SpO₂ greater than or equal to 96% on Room Air
	1	96% > SpO₂ ≥89% on Room Air
	2	SpO₂ < 89% on Room Air
Total Score		

*An amalgam of multiple clinical scores [12-17].

**Modified from Breathlessness, Cough, and Sputum Scale (BCSS) [18].

***Modified from Fatigue Severity Scale (FSS) [19].

This primary analysis will be performed in the cocci-positive per-protocol population of subjects who meet the case definition of coccidioidomycosis pneumonia and who were adherent to the intervention administration (See Section 11.4.1). As defined below, adherence will be defined as taking at least 80% of the study medication (fluconazole or placebo) as determined at the day 22 visit. Pill count, if available, will take precedence over patient report of adherence.

Case Definition

The case definition of coccidioidomycosis pneumonia is met if the is subject diagnosed with CAP at the time of enrollment as determined by the referring health care provider, and meets one of the following serologic criteria:

1. The patient is positive for any two serologic tests at any time point from Day 1 through Day 29. The two positive results can but do not necessarily have to be from the same assay or the same time point. The assays considered for this criteria are: Immunodiffusion testing [IDTP (IgM) and IDCF (IgG)]; Enzyme linked immunoassay testing (EIA-IgM and EIA-IgG); OR
2. The patient is negative for anti-*Coccidioides* antibody by immunodiffusion assay (or EIA-IgG) at Day 1 and sero convert to positive for anti-*Coccidioides* antibody by immunodiffusion assay (or EIA-IgG) at any time point after Day 1 through Day 29; OR
3. The patient is negative or indeterminate for anti-*Coccidioides* antibody by CF assay on Day 1 and demonstrates a titer of greater than or equal to 2 by CF assay at any point after Day 1 through Day 29; OR
4. The patient is positive for anti-*Coccidioides* antibody by CF assay on Day 1 and demonstrates a rise of greater than or equal to 2-fold dilution in Complement Fixation (CF) titer compared to baseline at any time point after Day 1 through Day 29.

All serologic testing for a single participant from Day 1 through Day 29 will be batched and run concurrently to eliminate confounding due to test run variability.

Adherence

Adherence in all subjects will be assessed by patient self-report and pill count according to standard procedures, on Days 22, 29 and 43. Pill count, if available, will take precedence over patient report. If pill count is not available, patient report will be used.

To be considered adherent at a visit when the clinical response is measured, the subjects will need to have taken at least 80% of their expected pills.

Secondary analyses of the primary objective will be performed in multiple analysis populations (see Section 11.4.1).

3.2.2. Secondary

See Section 11.4.4.2 for a discussion of the analysis populations utilized for the secondary outcome measures.

Secondary Outcome 1:

- The proportion of subjects who achieve a clinical response at Day 22 in each treatment group, including in all randomized subjects who took at least one dose of study medication.
 - “Clinical response” is defined as at least a 50% reduction in composite FLEET CAP score from baseline.

Secondary Outcome 2:

- The proportion of subjects who achieve a clinical response at Day 43 in each treatment group, including in all randomized subjects who took at least one dose of study medication.
 - “Clinical response” is defined as at least a 50% reduction in composite FLEET CAP score from baseline. Note that a subject who responds earlier before Day 43 does not need to achieve a clinical response at Day 43, as well.

Secondary Outcome 3:

- The mean, median, and quartiles of the FLEET CAP score at Days 22, 29 and 43 in each treatment group.
- The mean, median, and quartiles for each component of the FLEET CAP score at Days 22, 29 and 43 in each treatment group.
 - Cough
 - Fatigue
 - Chest Pain
 - Dyspnea (Shortness of breath)
 - Sputum production
 - Night Sweats
 - Fever
 - Hypoxia

Secondary Outcome 4:

-
- Number of days of school or work missed due to illness after the start of the treatment through Day 43 in each treatment group.
 - The mean, median, and quartiles for the mental component summary (MCS) and physical component summary (PCS) scores of the SF-12v2 instrument and the responses to the individual items of the PROMIS Item Bank v2.0 - Ability to Participate in Social Roles and Activities - Short Form 4a at Days 22, 29, 43, 90 and 180 in each treatment group.

Secondary Outcome 5:

- Incidence rate of all-cause mortality after the start of treatment and through Day 43 by treatment group.
 - Mortality information will be obtained through medical records or next of kin.

Secondary Outcome 6:

- The proportion of subjects who achieve a clinical response at Day 22 among all randomized subjects, regardless of coccidioidomycosis status or adherence to study drug, in each treatment group.

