The Extra-Pulmonary Symptom Score will be used to rate arthralgia, rash, and headache and will be completed by the subject on Days 1, 22, 29, and 43. After appropriate education on self-measurement using the visual analog scale, coccidioidomycosis positive subjects will be asked to complete this on Day 90 and 180 and return by mail to the study team.

The SF-12v2 uses 12 questions to measure functional health and well-being from the study subject's perspective across eight domains: physical functioning, role, bodily pain, general health perceptions, vitality, social functioning, emotional role, and mental health. The SF-12v2 will be completed by the subject on study Days 1, 22, 29, and 43. For subjects who are coccidioidomycosis positive, the survey will also be collected on Days 90 and 180.

The PROMIS Ability to Participate in Social Roles and Activities - Short Form 4a uses 4 questions to measure the subject's ability to participate in social roles and activities in the context of family, friends, leisure, and work. The PROMIS short form will be completed by the study subjects on study Days 1, 22, 29 and 43. For subjects who are coccidioidomycosis positive, the survey will also be collected on Days 90 and 180.

On study Days 22, 29, and 43, subjects will be queried about time missed from school or work due to illness.

See Section 6.7 for information regarding rescue procedures.

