
(SO 4): To assess the impact of early empiric antifungal therapy with fluconazole on days lost from work or school and responses to the SF-12v2 and PROMIS Item Bank v2.0 - Ability to Participate in Social Roles and Activities - Short Form 4a in subjects with coccidioidomycosis pneumonia.
	
Number of days of school or work missed after the start of the treatment through Day 43 in each treatment group.
 
The mean, median, and quartiles for the mental component summary (MCS) and physical component summary (PCS) scores of the SF-12v2 instrument and the responses to the individual items of the PROMIS Item Bank v2.0 - Ability to Participate in Social Roles and Activities - Short Form 4a at Days 22, 43, 90 and 180 in each treatment group.
	
Descriptive and/or graphical summaries of the outcome measures by treatment group. This analysis will be performed in both PP populations, both mITT populations, and the ITT population.

(SO 5): To assess the effect of early empiric antifungal therapy with fluconazole through Day 43 in subjects with coccidioidomycosis pneumonia on all-cause mortality by treatment group.
	
Incidence rate of all-cause mortality after the start of treatment and through Day 43 by treatment group.
	
Descriptive summaries of the outcome measure by treatment group. This will be performed in both PP populations, both mITT populations, and the ITT analysis population.

(SO 6): To assess whether early empiric antifungal therapy with fluconazole at Day 22 is non-inferior to placebo as defined by clinical response at Day 22 in all randomized subjects, regardless of coccidioidomycosis pneumonia status or adherence with study intervention, with baseline and follow-up FLEET-CAP scores.
	
Proportion of clinical response at Day 22 among all randomized subjects, regardless of coccidioidomycosis status or adherence with study drug, in each treatment group.
	
Two-sided level .05 test of non-inferiority based on whether the 95% confidence interval for the difference in estimates of 22-day response proportions excludes an absolute difference of .05 in favor of the placebo arm. This analysis will be performed in the ITT population.

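### Secondary Outcome 4 reports the four-question PROMIS form only item by item, so SO 4 has no single result on social participation; a score should be named, with the items kept as supportive.

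*Combined protocol and SAP*

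**What the plan says.** Section 3.2.2, Secondary Outcome 4, treats its two questionnaires differently within one sentence. For the SF-12v2 the measure is the "mental component summary (MCS) and physical component summary (PCS) scores of the SF-12v2 instrument". For PROMIS it is "the responses to the individual items of the PROMIS Item Bank". Table 11 (Section 11.4.4.2, SO 4) repeats the item-level definition, so it is not a slip in one place. No PROMIS total, mean or scale score appears anywhere in the document.

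Section 8.1 introduces the instrument with "Short Form 4a uses 4 questions to measure" and gives the thing measured as "ability to participate in social roles and activities in the context of family, friends, leisure, and work".

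The visit lists differ. Section 3.2.2 has "Short Form 4a at Days 22, 29, 43, 90 and 180 in each treatment group", while Table 11 has "Short Form 4a at Days 22, 43, 90 and 180 in each treatment group", without Day 29. Under Section 8.1, the Day 90 and Day 180 questionnaires go only to coccidioidomycosis-positive subjects.

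The planned analysis in Table 11 is "Descriptive and/or graphical summaries of the outcome measures by treatment group", in both per-protocol populations, both mITT populations and the ITT population. Section 11.4.4.2 leaves further detail to a separate statistical analysis plan, whose text is not in the document supplied.

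**The concern.** When four questions measure one construct, the natural outcome is one score. With items alone, SO 4 has no stated reading if two items favour fluconazole and two do not. A reader could put weight on whichever item or visit looks best. A single item is also usually a noisier measure of the construct than a score built from all four.

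The plan does not treat its other instruments this way. The SF-12v2 is reduced to two summary scores. FLEET CAP (Secondary Outcome 3 and Exploratory Outcome 4) and the Extra-Pulmonary Symptom Score (Exploratory Outcome 2) are each reported as a composite with their components beside it. PROMIS alone has components and no composite, and no reason is given. Exploratory Outcome 5 then repeats the secondary analyses under the alternative case definition, which multiplies the item-level output again.

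At stake is how clearly one secondary objective can be answered. The primary analysis is not affected.

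**Working it through.** The plan gives no SD, effect size, precision or power for PROMIS, so there is no stated figure to reproduce. Two things can be checked.

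**1. Number of by-arm summaries.** Inputs: four items (Section 8.1); five post-baseline visits in Section 3.2.2 or four in Table 11; Days 90 and 180 in cocci-positive subjects only (Section 8.1).

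| Population type | Visit list | Items only | One score |
|---|---|---|---|
| Cocci-positive (PP, mITT) | Section 3.2.2 | 4 × 5 = 20 | 5 |
| Cocci-positive (PP, mITT) | Table 11 | 4 × 4 = 16 | 4 |
| All-randomized (PP, mITT, ITT), visits covering everyone | Section 3.2.2 | 4 × 3 = 12 | 3 |
| All-randomized (PP, mITT, ITT), visits covering everyone | Table 11 | 4 × 2 = 8 | 2 |

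**2. Precision of a score against one item.** Three assumptions are needed, none of them in the documents: equal item variances, a common correlation r between items, and the same treatment effect on every item.

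- Variance of the four-item mean relative to one item = (1 + 3r)/4.
- SD ratio = √[(1 + 3r)/4].
- Equivalent gain in subjects = 4/(1 + 3r) − 1.
- 95% CI half-width for the arm difference, in single-item SDs, with 100 per arm (the cocci-positive per-protocol target in Section 11.2.1) = 1.96 × √(2/100) × SD ratio. For a single item this is 0.277.

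| r | Variance ratio | SD ratio | Gain in subjects | CI half-width |
|---|---|---|---|---|
| 0.5 | 0.625 | 0.79 | 60% | 0.219 |
| 0.7 | 0.775 | 0.88 | 29% | 0.244 |
| 0.8 | 0.850 | 0.92 | 18% | 0.256 |
| 0.9 | 0.925 | 0.96 | 8% | 0.267 |

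**What happens if the effect is not common.** Suppose only one item responds. The effect on the mean is a quarter of that item's effect, so the standardised effect on the score is (1/4)/√[(1 + 3r)/4] of it: 0.25/0.79 = 0.32 at r = 0.5 and 0.25/0.92 = 0.27 at r = 0.8. Compared with that one item, the score then loses signal. The general condition is that the average effect over the four items, as a fraction of the largest item effect, must exceed the SD ratio for the score to beat the best item. Nothing in the plan says in advance which item that would be.

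**The case against.** The strongest reply is that nothing inferential hangs on this outcome. SO 4 has no test, alpha, power or decision attached, and the trial is sized on the Day 22 clinical response. This stands. A reader might infer that the item-level plan inflates the type I error or costs the trial power. The documents do not support that, because no PROMIS hypothesis is tested. The equivalents in subjects describe precision only.

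A second reply is that the objective speaks of responses to the instrument, so item responses answer it literally. That is fair: the plan does not contradict itself here, and a score is an improvement rather than the repair of an error.

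A third is that the separate analysis plan may add a score. It may. However, what is deferred is analytic detail, whereas the outcome measure is already fixed as item responses in Section 3.2.2 and Table 11. A score added later would differ from the protocol's own outcome.

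A fourth concerns size, and it stands in full. The correlation is assumed. Four questions on one construct may well be highly correlated, which puts the gain near the low end. Section 8.1 also names four different contexts, so a common effect is not assured. A reader might take an 18% to 60% gain as established, or 20 summaries as applying to every population; neither holds. The gain is 8% at r = 0.9 and can reverse, and the count is 12 or 8 where only visits through Day 43 cover everyone.

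**Conclusion.** The point holds as a minor, optional improvement. The plan fixes the PROMIS outcome at item level in two places and names no score, while describing one construct and giving every other multi-item instrument a summary or composite. As a result SO 4 has no single PROMIS result. That conclusion rests on the text alone.

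The precision argument is secondary and conditional. It needs equal item variances, a common effect and an inter-item correlation that the documents do not supply.

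**What to change.** In Section 3.2.2 (Secondary Outcome 4) and Table 11 (SO 4), name one PROMIS score formed from the four items as the outcome at each visit, and summarise it by arm in the same way as MCS and PCS. State the scoring method and the rule for incomplete forms; the document has neither, so the sponsor must choose them. Keep the item responses as supportive summaries, following the pattern used for the FLEET CAP components. An arm difference with a 95% CI may be added, labelled as a descriptive estimate. While editing, reconcile the two visit lists, since Day 29 is in Section 3.2.2 but not in Table 11.

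The cost is a wording change to two protocol sections, with matching text in the separate analysis plan. All four items are already collected at the PROMIS visits, so no subject, visit or assessment is added. The downside is the extra scoring and missing-item rule.

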3.2.3. Exploratory

Exploratory Outcome 1:

- The time to first detection of positive anti-Coccidioides antibodies, as measured through Day 43 in each treatment group.
 - The results of antibody determination in concurrent testing of serial specimens by the following assays will be evaluated: Complement fixation (CF); qualitative immunodiffusion with CF antigen (IDCF); qualitative immunodiffusion with tube precipitin antigen (IDTP), and quantitative IDCF.

Exploratory Outcome 2:

- The mean, median, and quartiles of a composite Extra-Pulmonary Symptom Score at Days 22, 29, 43, 90 and 180 among subjects with coccidioidomycosis pneumonia, in the absence of disseminated disease, in each treatment group.
- The mean, median, and quartiles for each component of an Extra-Pulmonary Symptom Score (see [Table 3](#)) at Days 22, 29, 43, 90 and 180 among subjects with coccidioidomycosis pneumonia, in the absence of disseminated disease, in each treatment group
 - Arthralgia
 - Rash
 - Headache

Table 3: Extra-Pulmonary Symptom Score

Extra-Pulmonary Symptom Score	Points	Proposed Definition
Arthralgia*	0	None
	1	Mild (scored ≤ 3 on visual analog scale)
	2	Moderate (scored 4-6 on visual analog scale)
	3	Severe (scored 7-10 on visual analog scale)
Rash	0	Absent
	1	Covers less than one arm or one leg
	2	Covers more than one arm or one leg but does not itch
	3	Covers more than one arm or one leg and itches
Headache*	0	None
	1	Mild (scored ≤ 3 on visual analog scale)
	2	Moderate (scored 4-6 on visual analog scale)
	3	Severe (scored 7-10 on visual analog scale)
Total Score		

* Measurements on the visual analog scale will be rounded to the nearest cm for the purposes of assigning a score, where five-tenths will be rounded up.

Exploratory Outcome 3:

- The time to diagnosis of disseminated coccidioidomycosis, as measured through Day 180 after the start of the study among subjects with coccidioidomycosis pneumonia in each treatment group.
 - The diagnosis of disseminated disease in a case of coccidioidomycosis is defined as a diagnostic code of disseminated coccidioidomycosis given to the subject between Days 1 and 180 by the subject’s health care provider as determined by medical record review on Day 180.

Exploratory Outcome 4:

- The mean, median, and quartiles for the composite clinical FLEET CAP score and each of its individual components at Days 22, 29 and 43 in placebo recipients with coccidioidomycosis pneumonia.
 - Cough
 - Fatigue

- Chest Pain
- Dyspnea (Shortness of breath)
- Sputum production
- Night Sweats
- Fever
- Hypoxia

Exploratory Outcome 5:

- Repeat the analysis of the Primary Objective, and secondary objectives 1-6 with the alternative serologic case definition (see [Table 4](#)).

Table 4: Case Definition 2 (Alternative Case Definition for Exploratory Analyses)

Patients who meet at least one of the following criteria are considered cases [#] :
Patient is negative for anti- Coccidioides antibody by complement fixation (CF) assay on Day 1, and demonstrates a titer of greater than or equal to 2 by CF assay at both Days 22 and Day 29
Patient is negative for anti- Coccidioides antibody by complement fixation (CF) assay on Day 1, and demonstrates a titer of greater than or equal to 4 by CF assay at either Day 22 or Day 29
Patient is negative for anti- Coccidioides antibody by immunodiffusion CF (IDCF, IgG) on Day 1, and has a positive IDCF test on either Day 22 or Day 29
Patient is negative for anti- Coccidioides antibody by immunodiffusion TP (IDTP, IgM) on Day 1, and has a positive IDTP test on either Day 22 or Day 29
Patient is negative for anti- Coccidioides antibody by enzyme linked immunoassay testing (EIA-IgM) on Day 1, and has positive EIA-IgM at both Days 22 and Day 29
Patient is negative for anti- Coccidioides antibody by enzyme linked immunoassay testing (EIA-IgG) on Day 1, and has positive EIA-IgG at both Days 22 and Day 29
All serologic testing for a single participant from Day 1 through Day 29 will be batched and run concurrently to eliminate confounding due to test run variability.
Absolute values will be recorded for serologic tests, where appropriate, and Indeterminate/Equivocal test results will be treated as a Negative test.

Exploratory Outcome 6:

- The mean, median, and quartiles of the FLEET CAP score at Day 1 in subjects who meet the protocol defined primary case definition and subjects who do not meet the protocol defined primary case definition.

-
- The mean, median, and quartiles for each component of the FLEET CAP score at Day 1 in subjects who meet the protocol defined primary case definitions and subjects who do not meet the protocol defined primary case definition.
 - Cough
 - Fatigue
 - Chest Pain
 - Dyspnea (Shortness of breath)
 - Sputum production
 - Night Sweats
 - Fever
 - Hypoxia

Exploratory Outcome 7:

- The proportion of subjects who received at least one dose of the intervention and who exhibit an increase in liver function tests from baseline (pre-treatment Day 1) as defined as: confirmed AST elevation of >5X ULN or greater than or equal to 225 IU/L or ALT elevation of >5X ULN or greater than or equal to 250 IU/L or total bilirubin elevation >1.5X ULN or aminotransferase elevation of >3X ULN accompanied by total bilirubin elevation >1.5X ULN.

Exploratory Outcome 8:

- The adherence to long term self-administration of daily medications will be assessed in this order of precedence:
 - First: The mean number of pills taken as assessed by pill-count on Days 22, 29 and 43.
 - Second: Subject self-reported adherence as reported on Days 22, 29 and 43.

Exploratory Outcome 9:

- The proportion of subjects with a detectable fluconazole level as assessed by blood test on Days 22 and 43 in fluconazole recipients.
 - Plasma fluconazole concentration will be determined by high-performance liquid chromatography (HPLC)

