2.3.2. Known Potential Benefits

One of the known potential benefits of this clinical trial is that all participants will have knowledge of their coccidioidomycosis serologic status. Additionally, there is potential that early empiric therapy may clinically help those who have coccidioidomycosis pneumonia by more promptly treating pneumonia and reducing associated clinical symptoms and long-term sequelae of pneumonia and possible dissemination of infection to other body sites.

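### Exploratory Outcome 2 summarises extrapulmonary symptoms by arm only in cases free of dissemination, a post-randomisation event that fluconazole may reduce, so a benefit could be understated; an all-case summary is a cheap improvement

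*Combined protocol and SAP*

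**What the plan says.** Both bullets of Exploratory Outcome 2 in protocol section 3.2.3, one for the composite and one for its components, define the summaries among coccidioidomycosis cases "in the absence of disseminated disease, in each treatment group". The composite is summarised by mean, median and quartiles: "composite Extra-Pulmonary Symptom Score at Days 22, 29, 43, 90 and 180". Section 4 repeats the restriction, so it is deliberate.

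The matching objective in section 3.1.3 is wider: "To assess the effect of early empiric fluconazole therapy on the development of extrapulmonary symptoms associated with coccidioidomycosis pneumonia". It asks about a treatment effect and does not exclude disseminated cases.

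Dissemination is an outcome in its own right. Exploratory Outcome 3 is "The time to diagnosis of disseminated coccidioidomycosis, as measured through Day 180 after the start of the study", defined by "a diagnostic code of disseminated coccidioidomycosis given to the subject between Days 1 and 180" and found "as determined by medical record review on Day 180". Section 2.3.2 lists among the hoped-for benefits of early therapy a reduction in "possible dissemination of infection to other body sites".

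**The concern.** The restriction selects subjects on something that happens after randomisation and that the study drug may change. The subjects left in each arm need not be alike even though the arms were randomised.

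The expected direction is against fluconazole. If the drug prevents some dissemination, and disseminated cases have more headache, rash or joint pain, more high scorers leave the placebo summary than the fluconazole summary. A subject kept free of dissemination by fluconazole stays in, while the comparable placebo subject is removed. The objective asks for the effect on these symptoms, and the restricted summary can miss part of it.

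The timing of the exclusion is also undefined. Scores begin at Day 22, and Exploratory Outcome 2 gives no date by which dissemination must be absent.

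What is at stake is the reading of one exploratory, descriptive table.

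**Working it through.** **No stated figure to reproduce.** The documents give no dissemination rate, score gap, standard deviation or power for this outcome. The point rests on the definitions; the arithmetic only shows the likely scale.

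**Can the exclusion depend on treatment?** Yes. The event can fall anywhere from Day 1 to Day 180, and its prevention is a stated hope (sections 3.2.3 and 2.3.2).

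**Is the exclusion forced by missing data?** No. Under section 5.3.3.1 a subject diagnosed with dissemination stops study drug but remains in follow-up. Sections 7.3.5, 7.3.6 and 8.1 schedule the score at Days 90 and 180 for all cocci-positive subjects.

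**Does anything else correct it?** No. The selection-bias check in section 11.4.4.1 compares the number of coccidioidomycosis cases per arm, not dissemination. Exploratory Outcome 3 would show an imbalance in dissemination but leaves the score comparison as it is.

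**Scale.** From the documents: three components scored 0 to 3 (Table 3), so a range of 0 to 9; 100 evaluable subjects per arm (section 11.2.1). Assumed: placebo dissemination rate pP; fluconazole rate pF = pP/2; mean gap g of 3 or 5 points between disseminated and other cases; within-group SD 2; the same mean in both arms for everyone who does not disseminate.

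- All-case difference (placebo minus fluconazole) = (pP - pF) x g. Under these assumptions the restricted difference is 0, so this whole amount is lost.
- Variance per arm = 2² + p(1 - p)g². SE = √[(varP + varF)/100].

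| pP / pF | Lost, g = 3 | Lost, g = 5 | Lost/SE, g = 3 | Lost/SE, g = 5 |
|---|---|---|---|---|
| 2% / 1% | 0.03 | 0.05 | 0.10 | 0.17 |
| 4% / 2% | 0.06 | 0.10 | 0.21 | 0.33 |
| 6% / 3% | 0.09 | 0.15 | 0.30 | 0.47 |
| 10% / 5% | 0.15 | 0.25 | 0.49 | 0.74 |

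Example, 6% / 3% with g = 5: varP = 4 + 0.06 x 0.94 x 25 = 5.41; varF = 4 + 0.03 x 0.97 x 25 = 4.73; SE = √(10.14/100) = 0.32; lost = 0.03 x 5 = 0.15; ratio 0.47.

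**Can the sign change?** Yes, if subjects whose dissemination is prevented still score above the rest. Assume a mean of 2 in those who would never disseminate, 6 in disseminated cases, 4 in prevented cases, and rates of 10% and 5%.

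- All cases: placebo 2 + 0.10 x 4 = 2.40; fluconazole 2 + 0.05 x 4 + 0.05 x 2 = 2.30; difference +0.10, favouring fluconazole.
- Restricted: placebo 2.00; fluconazole 2 + 2 x 0.05/0.95 = 2.105; difference -0.105.

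If fluconazole does not change dissemination, both differences are 0 in this set-up.

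**Timing.** The rate that matters is the cumulative rate at the date when absence is judged. Judged visit by visit, few subjects would be out at Day 22 and the early summaries would barely move. Judged through Day 180, every summary from Day 22 on carries the full exclusion. By Day 180 the two readings essentially coincide.

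**The case against.** The strongest defence is that the restriction has a purpose. The objective concerns symptoms that accompany coccidioidal pneumonia; dissemination has its own objective and outcome; and headache, rash and joint pain can come from disseminated infection. Pooling mixes the two sources. This stands as a reason to keep the restricted table, but not as a reason to make it the only one under an objective about treatment effect.

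The outcome is also exploratory and specified as descriptive statistics, with no test or estimated difference. That limits the importance of the point and is accepted.

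Sections 11.4.4 and 11.4.4.3 leave the exploratory analyses to a separate statistical analysis plan, which might add an all-case summary. It might, but the restriction is written into the outcome definition, and deferring methods does not remove it.

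A reader might infer that a diagnosis near Day 180 deletes the same subject's Day 22 score. The documents do not say so. The Day 180 record review belongs to the definition under Exploratory Outcome 3, and sections 7.3.1 to 7.3.3, 7.3.5 and 7.3.6 ask about dissemination at Days 22, 29, 43, 90 and 180. Judging absence as of each visit is an equally available reading and removes no earlier score. The supportable point is that the rule is undefined.

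A reader might also infer that this restriction alone makes the arms non-comparable. It does not act alone. Case status uses serology through Day 29, and after Day 43 subjects know their assignment and placebo cases are referred for possible treatment. An all-case summary repairs one of these problems, not all of them.

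**Conclusion.** The concern holds as a minor one. The restriction conditions a by-arm summary on a post-randomisation event that treatment may reduce, and nothing else in the plan corrects for it. If fluconazole lowers dissemination and disseminated cases score worse, benefit is understated.

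The size is unknown and likely small if dissemination is uncommon: about 0.03 to 0.15 points at assumed placebo rates of 2% to 6%, halved on fluconazole, with a 3 to 5 point gap. Reaching 0.7 of a standard error takes a 10% rate and a 5-point gap together. These figures concern means and apply the gap to every subject who disseminates, so they suit visits after diagnosis best; medians and quartiles should move less when few subjects are removed.

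The documents do not support reading this as a threat to the trial's conclusions. Primary and secondary inference is unaffected.

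**What to change.** 1. Make the main version of Exploratory Outcome 2 a by-arm summary of the score in all cocci-positive cases, whatever their dissemination status.
2. Keep the restricted version as a labelled supplementary summary, and state that absence of dissemination is judged as of each visit.
3. Report the number excluded from the restricted version by arm and visit.

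A version that ranks disseminated subjects worst from diagnosis onward is optional. It makes the symptom score depend on a provider's diagnostic code and partly duplicates Exploratory Outcome 3.

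The cost is one changed analysis set and one extra table, with no new data collection. The downside is that the all-case version includes symptoms caused by disseminated disease; the supplementary table beside it shows the picture without those cases.
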